In-depth qualitative interviews with stimulant-using MSM. In-depth interviews with stimulant-using MSM will be approximately one hour and cover topics such as history of stimulant use, attitudes and beliefs about PrEP. Those who are not on PrEP will be asked to describe on barriers and facilitators to accessing PrEP. Those who are currently taking PrEP will be asked to describe how they successfully

IRB Study Number: 20180823

Version #10.1; April 2023

navigated the process of initiation and strategies they are implementing to achieve prevention effective PrEP adherence. After completing the interview, participants will complete a brief survey to assess demographic information and efforts to navigate the PrEP healthcare continuum (see attached). Stimulant-using MSM will receive \$40 for completing this one time study visit.

[figure not shown]
Phase II – We will conduct a pilot SMART with 70 HIV-negative, stimulant-using MSM who meet CDC criteria for PrEP eligibility.

First Stage Intervention. After completing a baseline assessment and a brief run-in period, participants will be randomized to complete a 3-month CM intervention or a two-session MI intervention that were developed as part of our Phase I activities.

Second Stage Intervention. Three months after this first-stage randomization, participants will complete a second informed consent prior to a 3-month follow-up assessment to determine whether they are responders.

[figure not shown]
Experimental Conditions. Responders will be classified as those who have started PrEP, the primary outcome. Responders will continue with assessments only.

Participants who have not responded to the initial intervention will be randomized again to either: 1) continue with assessments only; or 2) switch to the other intervention (i.e., CM+MI versus MI+CM). An overview of the pilot SMART procedures is provided in the figure below. Below we describe each of the procedures relevant to executing this pilot SMART.

Telephone screen. Stimulant-using MSM will complete a brief telephone screen to determine eligibility for enrolling in the pilot SMART based on inclusion criteria above for Phase II (see attached). This telephone screen has been modified to include items relevant to the novel coronavirus (COVID-19), which are also attached. The figure below describes the participant flow for the pilot SMART.

PRISM 2.0 Study Flow Diagram

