Non-reactive (HIV-) test results will be delivered to participants as part of their randomization visit. For those who do not respond to attempts to schedule their randomization visit, after 2 months their non-reactive HIV test results will be emailed to the email address on file via a secure, encrypted University of Miami email. This report does not contain any PHI.

All study staff also receive ongoing training and supervision from [name] (a licensed psychologist) on delivering HIV test results and providing counseling to individuals experiencing acute distress. All staff will receive training in procedures for immediate linkage to confirmatory HIV testing. Participants residing in Miami-Dade county who are test positive for HIV will be referred for confirmatory testing and anti-retroviral therapy (ART) with [name].

Randomization visit. Approximately one week after baseline, participants who are confirmed to be HIV-negative will attend a separate randomization visit. Those randomized to CM will be introduced to incentives for PrEP clinical evaluation and uptake. Participants randomized to MI will receive their first session of this intervention. All participants will receive a \$20 Amazon gift card or secure cash application payment for attending the randomization visit.

CM intervention protocol. Participant randomized to CM will complete a 3-month CM protocol where they will be eligible for CM incentives for documentation that they have been evaluated for PrEP by a medical provider (\$50) and filled a prescription for PrEP (\$50) in the three months following randomization. Total possible CM incentives are \$100 per participant, which will be provided in Amazon gift cards or secure cash application payment.

MI protocol. Participants in the MI intervention will complete two individually delivered sessions via zoom designed to enhance intrinsic motivation and self-efficacy for taking the first steps towards starting PrEP and addressing the

IRB Study Number: 20180823

Version #10.1; April 2023

intersection of substance use and HIV risk. Session 1 focuses on supporting efforts of participants to be medically evaluated for PrEP. Session 2 focuses on addressing the intersection of substance use and HIV risk. A detailed protocol for this 2-session MI intervention is attached. Participants will receive a \$20 Amazon gift card or secure cash application payment for completing each MI session via zoom.

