Stage 2 informed consent. Prior to completing the 3-month follow-up assessment, participants will provide informed consent for the Stage 2 of the pilot SMART. This consent will clarify that participants may be invited to participate in a CM or MI intervention based on the responses to the survey questions and prior intervention assignment. Due to the challenges presented by COVID-19, we are requesting a waiver of written consent to review the consent with participants over zoom.

3-month follow-up assessment with second-stage randomization. After completing the informed consent process, we will re-administer quantitative measures from the baseline assessment via Zoom, and those who have not started PrEP will be classified as non-responders. All non-responders will complete the second-stage randomization to either: 1) continue with assessments only; or 2) switch to the other intervention (CM+MI versus MI+CM). Those randomized to receive CM or MI will receive these intervention consistent with the protocols described above. Responders will continue with assessments only. Participants will receive a \$50 Amazon gift card or secure cash application payment for completing this assessment. Participants will have a 30-day window (+1 month) to complete their follow-up assessments.

6-month follow-up assessment. We will re-administer the quantitative measures from the baseline assessment and a qualitative exit interview (see attached) via zoom. Participants will receive a \$50 Amazon gift card or secure cash application payment for completing this assessment. Participants will have a 30-day window (+1 month) to complete their follow-up assessments.

6) Risks

These study procedures meet the criteria for minimal risk research activities. However, possible risks include: 1) a breach of confidentiality; and 2) negative psychological reactions to study procedures.

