Because this is a pilot study, we have not conducted a formal power analysis. In fact, there is increasing recognition in clinical research methods that pilots should focus primarily upon issues relevant to feasibility and acceptability of a more definitive study, not effect size estimation.

Feasibility. To evaluate feasibility of a more definitive trial, we will monitor rates of recruitment and effort required (e.g. number of staff hours) as well as the number of screenings conducted, proportion eligible, and proportion who agree to enroll. *Feasibility of recruitment* will be operationalized as an enrollment rate of 70% or higher, an established standard in the literature. We will also record number of rescheduled and missed assessment visits, CM visits, and MI sessions to estimate staffing needs and retention protocols for a planned R01. *Feasibility of intervention delivery* will be operationalized as attending three-fourths of scheduled MI sessions (3 of 4 sessions completed on average). Although power will be limited, we will conduct independent samples t-tests to describe the average number of MI sessions attended among non-responders randomized to switch (i.e., CM+MI vs. MI+CM).

Acceptability. To measure *acceptability*, we will modify previous intervention satisfaction evaluation surveys that have been administered to methamphetamine users in [name] clinical research. Measures include items such as, "How satisfied were you with the program in general?" and "How likely are you to recommend this intervention to a friend who uses stimulants?" Independent samples t-tests will describe mean acceptability ratings of CM and MI among non-responders who are randomized to switch (i.e., CM+MI vs. MI+CM).

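### The switcher-only t-test of MI sessions mixes timing and post-assignment selection with delivery; report attendance for everyone assigned MI, by stage

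*Protocol*

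**What the plan says.** Protocol section 5 (First Stage Intervention) says that "participants will be randomized to complete a 3-month CM intervention or a two-session MI intervention". Under Randomization visit, "Participants randomized to MI will receive their first session of this intervention", so session 1 for MI-first men falls on the day of first-stage assignment.

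The second stage comes later: "Three months after this first-stage randomization, participants will complete a second informed consent prior to a 3-month follow-up assessment". At that visit "those who have not started PrEP will be classified as non-responders". Under Experimental Conditions, "Participants who have not responded to the initial intervention will be randomized again to either" assessments only or a switch to the other intervention. For the rest, "Responders will continue with assessments only".

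Section 8, Feasibility, then does three separate things:

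- It records missed and rescheduled visits and sessions in order to estimate staffing.
- It sets a delivery criterion of three-fourths of scheduled MI sessions, glossed as three of four.
- While conceding limited power, it adds that "we will conduct independent samples t-tests to describe the average number of MI sessions attended among non-responders randomized to switch", comparing CM+MI with MI+CM.

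The SAP's Feasibility paragraph reports completion of MI and CM sessions. It mentions neither a t-test nor a restriction to switchers, and it gives no denominator.

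**The concern.** The two groups look alike because both consist of non-responders assigned to switch, but they meet the selection events at different points relative to MI.

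- **MI+CM.** MI is delivered in months 0 to 3. Whether a man is counted depends on what he does afterwards: staying in the study, consenting to Stage 2 and not having started PrEP. If better attenders are more likely to reach month 3, the group mean rises. If better attenders are more likely to start PrEP and leave the set, it falls.
- **CM+MI.** The same events have already happened when MI is offered, so every man assigned is counted whatever he then attends.

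Second-stage randomization compares switching with assessments only, within each first-stage arm. First-stage randomization compares all MI-first men with all CM-first men. Neither makes the two switch groups comparable once the set is conditioned on retention and response.

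This is the only between-group comparison of MI attendance in the feasibility plan of a pilot meant to inform a larger SMART. A difference, or the lack of one, could be taken to show that MI is easier to deliver first or second. The contrast cannot support that. The attendance of MI-first men who responded, stayed on assessments only or were lost would also go unused in it.

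**Working it through.** The plan gives no expected number of switchers, response rate or retention rate, so there is no figure of its own to reproduce.

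**Inputs.** From the protocol: "We will conduct a pilot SMART with 70 HIV-negative, stimulant-using MSM" and two MI sessions per man assigned to MI. Assumed: 1:1 allocation at both stages (neither ratio is stated), hence 35 MI-first men; first-stage response r from 0% to 50%; loss L by month 3 from 0% to 20%.

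**1. How many MI-first men enter the test.** n = 35 × (1 − L) × (1 − r) × 0.5.

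| Response r | Loss L | Men in test | Share of 35 left out |
|---|---|---|---|
| 0% | 0% | 17.5 | 50% |
| 20% | 10% | 12.6 | 64% |
| 20% | 20% | 11.2 | 68% |
| 30% | 10% | 11.0 | 68.5% |
| 30% | 20% | 9.8 | 72% |
| 50% | 20% | 7.0 | 80% |

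Half is the best case under 1:1. To keep more than half, the switch share would have to exceed 0.5 / [(1 − r)(1 − L)]. At r = 20% and L = 20% that is 0.5 / 0.64 = 78%.

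**2. How far selection could move MI-first attendance.** Let a be true second-session attendance, R_a and R_n retention in attenders and non-attenders, and p_a and p_n their response rates. Attendance among retained non-responders is

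a·R_a·(1 − p_a) / [a·R_a·(1 − p_a) + (1 − a)·R_n·(1 − p_n)].

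Take a = 0.70, with all rates assumed:

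- Attenders respond more (R_a = R_n = 0.9, p_a = 0.45, p_n = 0.10): 0.3465 / (0.3465 + 0.2430) = 0.588.
- Attenders stay more (R_a = 0.95, R_n = 0.60, p_a = p_n = 0.30): 0.4655 / (0.4655 + 0.1260) = 0.787.
- Attendance unrelated to either: 0.70, no shift.

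On the 0-to-2 scale, reweighting three assumed attendance distributions shifts the MI-first mean by +0.06 to +0.35 sessions when only retention depends on attendance. The shift is −0.05 to −0.23 when only response does, and +0.02 to +0.13 in the scenarios with both. The sign is not fixed.

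**3. Timing of session 1.** Suppose every MI-first man receives session 1 at the randomization visit and every other session is attended with probability p. The means are 1 + p for MI-first and 2p for CM-first, a gap of 1 − p with equal engagement: 0.40 at p = 0.60, 0.25 at p = 0.75, 0.10 at p = 0.90. The 3-month section says only that second-stage MI follows the same protocol. If that means session 1 at the 3-month visit, this gap may shrink or vanish, but the selection in step 2 remains.

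**4. Precision.** With two-sided 5% and 80% power assumed, the detectable difference is (1.96 + 0.84) × √(2/n) SD: 1.25 SD at n = 10 and 1.06 SD at n = 14. Power for 0.5 SD is 20% to 26%. More men would improve precision without removing the bias.

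**5. What the full denominator gives.** At 20% response and 20% loss, 35 + 11.2 = about 46 men are assigned MI at some stage, against 2 × 11.2 = about 22 in the test (48%).

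**The case against.** The strongest reply is that little hangs on this test. The protocol offers it as description, concedes limited power, says pilots should not estimate effect sizes, and attaches no threshold or decision to it. Switchers are the only men assigned both interventions, so describing them is reasonable. The SAP reports session completion without the test. All of this stands, and it limits the point to one contrast. It does not make the two groups comparable, and calling a difference descriptive does not tell a reader what it describes.

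Some stronger readings are tempting but not supported:

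- A reader might infer that the contrast measures survivor selection rather than delivery. The documents do not show that. Retention and response pull in opposite directions, the shifts in the working come from assumed rates, and there is none if attendance is unrelated to both.
- A reader might infer that the feasibility criterion or the staffing estimate rests on this selected minority. Section 8 states the criterion separately and bases staffing on recorded missed and rescheduled sessions; neither is limited to switchers.
- A reader might take the loss of most MI-first men as a fact of the design. It depends on a re-randomization ratio that is not stated.
- A reader might treat the SAP's statement that no tests were done as settling the matter. That sentence concerns primary and secondary outcomes, so the protocol's feasibility test is dropped only by silence.

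**Conclusion.** The concern holds for the protocol's switcher-only contrast and no further. MI-first men are selected on retention, Stage 2 consent and non-response after their MI attendance, whereas CM-first men are selected before MI is offered; session 1 at the randomization visit may add a timing difference. The comparison should not be read as showing how well MI can be delivered first versus second. Barring exact cancellation, the bias is zero only if attendance is unrelated to retention and response and the timing of session 1 does not matter. Its size and sign are otherwise unknown.

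Under 1:1 re-randomization at least half of the MI-first men are excluded, and about 69% to 72% at an assumed 30% response and 10% to 20% loss. The effect on final reporting is limited, because the SAP describes session completion without this test. The change is still worth making, since it concerns the pilot's own central aim and costs almost nothing.

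**What to change.** 1. Delete the switcher-only t-test of MI sessions from the Feasibility paragraph in protocol section 8.
2. In the SAP's session-completion report, give counts of 0, 1 and 2 MI sessions attended, without a comparison, for (a) all men randomized to first-stage MI and (b) separately, all CM-first non-responders re-randomized to MI. Count each from that assignment, including men later lost.
3. Apply the three-fourths criterion to these two denominators. First reconcile its gloss of three of four sessions with the two-session MI in section 5 (First Stage Intervention and MI protocol); the passages do not agree as written.

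The cost is one deletion in the protocol, one added sentence in the SAP and the reconciliation of the session count. No new data are needed, because missed MI sessions are already to be recorded.

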PrEP Readiness Interventions for Supporting Motivation

[name], ABAP (Contact MPI) & [name], MPH (MPI)

NCT04205487

August 7, 2024

Feasibility. In this pilot SMART, we examined several indices of feasibility. We report randomization rates, completion of MI and CM sessions, fidelity ratings of MI sessions, and follow-up rates over six months.

Acceptability. After the 6-month assessment, participants were given the opportunity to sit for a one-on-one, semi-structured qualitative exit interview via Zoom. The staff member conducting exit interviews was not involved in the primary study procedures to avoid bias. Participants were given an overview of the activities they completed during PRISM (e.g., two MI sessions, CM incentives, and three surveys) and asked about their experiences. Interview guides were tailored to each participant's study arm (MI, CM, or MI+CM) and whether they had filled a PrEP prescription during the intervention (i.e., responders versus non-responders). Exit interviews were approximately 30 minutes and participants received a \$50 incentive.

Qualitative interviews were analyzed using a rapid qualitative analytic approach as a guide (Hamilton, 2020; Harkness et al., 2022). Interviews were first transcribed verbatim and reviewed for quality assurance. Transcriptions were then used to develop a matrix summary of participant responses, including participant number, intervention arm, PrEP status, and responses to each domain of interest. The research team, consisting of a graduate student research assistant, a doctoral level interviewer and a doctoral level project manager, reviewed and discussed the matrix to identify emerging themes, data consistency and matrix accuracy. Illustrative quotes were then extracted to highlight relevant themes. Finally, the manuscript authors reviewed the matrix, themes, and illustrative quotes as well as agreed upon the accuracy of the findings.

Scalability. The cost analysis was framed from the provider perspective to reflect the resources required to plan and implement the PRISM telehealth motivational enhancement interventions in a community-based setting (e.g., STI clinic). Cost data were collected from the study's financial records and interviews with the investigative team. We created a structured data extraction template to organize cost data and summarize key results including start-up costs (i.e., one-time investments required to implement the strategies), total intervention costs, and participant incentive payments. Resources were tracked across three stages of the intervention: baseline, first-stage intervention (three months), and second-stage intervention where applicable (six months). Total incentive payments for each intervention stage were calculated by multiplying the number of participants engaged in each strategy by the payment amounts for each intervention stage. We excluded purely research-related expenses such as study recruitment efforts and outcome assessments. We focused on identifying the essential costs required to replicate the interventions outside of a research environment. Expense categories comprised personnel (including wages and benefits), consultants, clinical assessments, and incentives. Fixed expenses like infrastructure (e.g., buildings and facilities), utilities, transportation, and equipment were not applicable since all interactions were conducted remotely via Zoom and data organized in REDCap. The only direct expenses were for supplies (i.e., HIV tests, shipping, and computers).

PRISM primary and secondary outcomes. Adaptive interventions that are embedded in a SMART can be compared via the Weighted and Replicated (W&R) method (Nahum-Shani et al., 2012). However, given the feasibility and acceptability nature of this study we instead descriptively compared three groups by aggregating across the first-stage and second-stage randomizations (see Figure 1): MI-only (arms D and E), CM-only (arms A and B), and MI+CM (arms C and F). Specifically, our efforts to examine the primary and secondary outcomes proceeded in four steps. First, demographic characteristics and meth use severity were stratified by first-stage randomization status (i.e., MI versus CM) to ensure randomization was successful (see Table 1). Second, intervention assignment was collapsed into the three groups described above. Third, because pilot trials do not provide reliable effect size estimates (Kraemer & Kupfer, 2006), we did not conduct statistical tests or comment on the magnitude of CM, MI, or MI+CM effects. Instead, we provide descriptive statistics for primary and secondary outcomes at six months stratified by intervention assignment. Fourth, we examined correlates of verified PrEP use (versus no PrEP use) over the 6-month follow-up, irrespective of first- or second-stage randomization status.

Figure 1. Pilot SMART procedures

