**PrEP Readiness Interventions for Supporting Motivation
(PRISM)**

**[name], ABAP (Contact MPI) & [name],
MPH (MPI)**

NCT04205487

August 7, 2024

UM-IRB

20180823: Stimulant-Using MSM and PrEP

(PRISM project)
[name], Principal Investigator

NCT04205487

Version Number #10.1

Version Date: 04/2023

IRB Study Number: 20180823
Version #10.1; April 2023

1) Protocol Title

Adaptive Intervention Strategies to Optimize PrEP Clinical Evaluation and Uptake in Stimulant-Using Men

2) Objectives*

The overarching goal of this formative research is to examine whether—and in what combination—contingency management (CM) and motivational interviewing (MI) can facilitate entry of stimulant-using men who have sex with men (MSM) into the pre-exposure prophylaxis (PrEP) care continuum.

- Aim 1.** Augment CM and MI with content to facilitate entry into the PrEP care continuum by conducting qualitative interviews with PrEP healthcare team members and stimulant-using MSM.
- Aim 2.** Examine the *feasibility and acceptability* of adaptive treatment strategies combining CM with MI to promote clinical evaluation for PrEP, PrEP uptake, and PrEP care retention.
- Aim 3.** Document implementation factors relevant the *scalability* of CM and MI such as perceptions of community-based HIV prevention providers to inform a full-scale sequential multiple assignment randomized trial (SMART) of the interventions.

3) Background*

Preliminary Data: There are no relevant preliminary data for this R34 project where the primary objective is to obtain preliminary data for a planned R01 proposal.

Significance: The CDC estimates one-in-six MSM will acquire HIV in their lifetime, including one-in-two Black MSM and one-in-four Hispanic/Latino MSM. PrEP is highly effective for preventing HIV infection, but many MSM who are at elevated risk for HIV are experiencing difficulties with initiating and remaining on PrEP. As a biomedical intervention, PrEP offers tremendous protection against HIV infection without necessitating changes in sexual behavior. PrEP can also serve as a gateway into regular HIV testing as well as comprehensive sexual and mental health care. There is an urgent need to augment as well as tailor evidence-based CM and MI interventions to facilitate entry of stimulant-using MSM into the PrEP continuum.

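### The cost analysis aims at replication cost but reports study totals, which depend on the trial's headcounts and second-stage randomisation; it names no unit cost per participant or expected cost per sequence

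*SAP*

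**What the plan says.** The SAP (Scalability) takes the provider's viewpoint in a community setting and states its purpose as follows: "We focused on identifying the essential costs required to replicate the interventions outside of a research environment". A data extraction template is used to "summarize key results including start-up costs (i.e., one-time investments required to implement the strategies), total intervention costs, and participant incentive payments". Resources are tracked at baseline, first stage and, where it applies, second stage. Incentive totals are the number of men engaged in each strategy times the payment for the stage. Expenses that exist only for research, such as recruitment and outcome assessment, are removed. No cost per participant is named, and no expected cost of a sequence.

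The Protocol (section 5, Procedures Involved) describes the design that generates these costs: "We will conduct a pilot SMART with 70 HIV-negative, stimulant-using MSM". At the first stage "participants will be randomized to complete a 3-month CM intervention or a two-session MI intervention". At three months, "Responders will be classified as those who have started PrEP, the primary outcome". Responders continue with assessments only; non-responders "will be randomized again to either: 1) continue with assessments only; or 2) switch to the other intervention". Neither document gives the allocation ratio at either stage or an expected response rate.

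**The concern.** Second-stage intervention spending arises only for non-responders randomised to switch. The men sent to assessments only are there because the trial needs a comparison. A clinic following a start-with-one, switch-if-PrEP-not-started sequence would have no such group. The SAP strips out other research-only items but makes no adjustment for this one.

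A study total also carries the trial's headcounts: how many men entered each arm and how many responded. A clinic with different numbers cannot use the total without unit costs, response proportions and switch shares, and the SAP does not list these as results. What is at stake is whether the figures serve the SAP's own replication purpose and help in planning the later full-scale trial that Aim 3 is meant to inform.

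**Working it through.** **Inputs**
- CM incentives (Protocol section 5, CM intervention protocol): $50 for evaluation + $50 for a filled prescription = $100, which reproduces the stated maximum.
- MI payments (Protocol section 5, MI protocol): 2 sessions x $20 = $40.
- Sample size: 70 planned. There is no power or total-cost calculation to reproduce ("Because this is a pilot study, we have not conducted a formal power analysis").
- Assumptions: 1:1 first-stage allocation (35 per arm); share switched s = 0.5, range 0.33 to 0.67; response rate r between 20% and 60%, equal in both arms.
- The documents give no personnel, consultant, assessment or supply amounts, so the dollar figures cover incentives only, at maximum payout. The $20 for the randomisation visit is left out because it is the same in both arms.

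**Within a first-stage arm.** Let a be the first-stage and b the second-stage unit cost.
- Study cost per starter = a + s(1 − r)b
- Full sequence per starter = a + (1 − r)b

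The study figure is lower whenever r < 1 and s < 1, for any positive b. The second-stage part must be multiplied by 1/s: about 3.0 at s = 0.33, 2.0 at s = 0.5 and 1.5 at s = 0.67.

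With s = 0.5:

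| r | MI then CM: study | MI then CM: sequence | CM then MI: study | CM then MI: sequence |
|---|---|---|---|---|
| 20% | 40 + 0.5 x 0.8 x 100 = $80 | $120 | 100 + 0.5 x 0.8 x 40 = $116 | $132 |
| 40% | $70 | $100 | $112 | $124 |
| 60% | $60 | $80 | $108 | $116 |

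The study figure is 25% to 33% lower for MI then CM (20/80 to 40/120) and 7% to 12% lower for CM then MI (8/116 to 16/132).

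**Pooled over both first-stage arms**, with s = 0.5:
- Pooled cost per entrant = 0.5(100 + 40) + 0.5 x 0.5(1 − r)(40 + 100) = 70 + 35(1 − r)
- r = 20%: $98, against $120 (MI then CM) and $132 (CM then MI)
- r = 60%: $84, against $80 and $116

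MI then CM equals the pooled figure when 40 + 100(1 − r) = 70 + 35(1 − r). That gives 1 − r = 30/65, so r is about 54%. Above that rate the pooled figure is too high for this sequence.

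**Sensitivity of the pooled comparison**
- If CM is paid only as earned (responders $100, non-responders $0 to $50), the reversal moves to a response rate of roughly 60% to 70%.
- If staff time made MI twice as costly as CM (an assumption), CM then MI would be the sequence that falls below the pooled figure. With C = 1 and M = 2: 1 + 2(1 − r) = 1.5 + 0.75(1 − r), so r = 60%.
- For MI alone with no switching, the pooled figure is too high: $91 against $40 at r = 40%.

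**The case against.** The strongest reply is that the SAP never undertook to cost a policy of switching every non-responder. Aim 3 concerns the scalability of CM and MI. The title ("Adaptive Intervention Strategies to Optimize PrEP Clinical Evaluation and Uptake in Stimulant-Using Men") and Aim 2 speak of adaptive strategies, but Aim 2 covers feasibility and acceptability. The Scalability section speaks of replicating the interventions. This stands, and it is why unit costs of CM and MI should come first, with sequence costs added as description. It does not rescue study totals, which are not the cost of replicating either intervention for a given number of clients.

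Stage-level tracking and the headcount-times-payment rule mean that a reader given those inputs could rescale the incentive totals. That also stands: the cost data are not shown to be wrong.

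This is also a descriptive pilot. With 35 men per arm and 40% response, the standard error of the response proportion is √(0.4 x 0.6/35) = 0.083. The 95% margin is then about 0.16, or $16 on the second-stage part of MI then CM (0.16 x $100). The expected costs will be imprecise and should be labelled so.

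The maximum-payout figures are a further weakness. A non-responder in the CM arm has not started PrEP and would ordinarily not have earned the prescription payment. The within-arm direction does not depend on this; the dollar amounts do.

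A reader might also infer that totals for MI, CM and MI+CM will be set against each other as unequal groups. The SAP uses that three-group collapse for primary and secondary outcomes and does not plan it for costs.

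**Conclusion.** The point holds as a defect in the quantity reported. Study totals reflect the trial's headcounts and randomisation mix, and the SAP names neither a per-participant nor a per-sequence cost. Within a first-stage arm, second-stage cost is too low by a factor of 1/s for a clinic that would switch every non-responder. That is two-fold if allocation is 1:1, which the documents do not state.

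A reader might go further and infer that the totals understate every switch sequence, or that the error always flatters the interventions. The documents do not support that. Against a pooled total the direction depends on the response rate and the CM-to-MI cost ratio; with maximum incentives and 1:1 at both stages it reverses for MI then CM above about 54% response. Start-up cost is one-time and does not depend on the switch share. The dollar figures are illustrations and not estimates of the study's costs.

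**What to change.** In the SAP's Scalability section:

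1. Report cost per participant for CM and for MI, by stage, including personnel and supply costs and the incentives actually paid. Show start-up cost separately and keep study totals as a supporting line.
2. Add, as a descriptive figure, the expected cost per person starting each sequence (MI then CM; CM then MI): first-stage unit cost + (proportion of first-stage starters classified as non-responders at the 3-month visit) x second-stage unit cost among men actually switched.
3. State the second-stage allocation ratio and the number switched in each first-stage arm.
4. State how men not classified at three months are counted. Stage 2 consent comes before the assessment that defines response, so men who are lost or decline are never classified. Keeping them in the denominator but not among non-responders gives them no second-stage cost; counting them as non-responders would charge for a second stage they may never enter.

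The cost is a few lines of SAP text and a small recalculation from resources already tracked by stage. No effect test is needed, so the descriptive approach is unchanged. The drawbacks are estimates that rest on few men per arm and a second-stage cost that looks less favourable than the study total.
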